8.2.2 Potential Hy's Law Cases

Study center personnel must report every patient who meets potential Hy's Law criteria from the time the ICF is signed until 30 days after the final protocol-defined study visit or the last known dose of study drug (if the final visit does not occur).

The criteria for potential Hy's law cases are as follows:

ALT or AST \geq 3 × ULN and

Total bilirubin $\geq 2 \times ULN$ and

Alkaline phosphatase $< 2 \times ULN$

Study center personnel must report every subject who meets these potential criteria. Typically, these analytes will be obtained from the same sample, but they may come from multiple samples taken within a 24-hour period. This requirement applies from the time the ICF is signed for the study until 30 days after the last known dose of study drug.

A laboratory alert for potential Hy's Laws cases will be in place, and the laboratory must notify Investigators and the Sponsor immediately when the above criteria have been met. The Sponsor must be notified of any potential Hy's Law case as soon as possible (within 24 hours of learning of a potential Hy's Law case). Refer to the SAE reporting procedures (Section 8.2.1.5.2) even if no AE has occurred.

Every effort to determine the cause of the liver enzyme abnormalities must be made, and close monitoring should be initiated in conjunction with the Study Physician and in accordance with the FDA Guidance for Industry: Drug Induced Liver Injury—Pre-Marketing Clinical Evaluation (July 2009).

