Alkaline phosphatase	U/L	_	≥ 2 × ULN		
ALT	U/L	_	≥ 3 × ULN		
AST	U/L	_	≥ 3 × ULN		
Blood urea nitrogen (BUN)	mg/dL	_	≥ 30		
Calcium	mg/dL	< 7	> 12		
Chloride	mEq/L	< 90	> 115		
Total Cholesterol	mg/dL	_	≥ 300		
СРК	mg/dL	_	≥ 5 × ULN		
Creatinine	mg/dL	_	> 1.3 × ULN		
Glucose	mg/dL	< 45	> 160		
LDL Cholesterol	mg/dL	_	> 200		
Potassium	mEq/L	< 3	> 5.5		
Prolactin	ng/ml	_	> 200		
Sodium	mEq/L	< 130	> 150		
Total bilirubin	mg/dL	_	≥ 2 × ULN		
Total protein	_	< 0.9 × LLN	> 1.1 × ULN		
Triglycerides	mg/dL	_	≥ 300		
Uric Acid	mg/dL	_	> 1.1 × ULN		
Urinalysis					
Protein	_	_	At least 2 +		
Glucose	_	_	At least 2 +		
Blood	_	_	At least 2 +		

ALT = alanine aminotransferase; AST = aspartate aminotransferase; CPK=creatine phosphokinase; LLN = lower limit of normal of laboratory reference range; PCS = potentially clinically significant; ULN = upper limit of normal of laboratory reference range.

Confidential Page 21 of 40

^a Criteria refer to conventional units.

The number and percentage of patients with shifts from baseline at the end of Open-label Treatment Period according to normal range and PCS criteria (PCS Low, Low, Normal, High, PCS High) for each parameter will be provided if applicable.

The criteria for elevated liver function-related laboratory values are specified in Table 10-3. The frequency and percentage of subjects with treatment-emergent elevated liver function values during the Open-label Treatment Period will be summarized for each treatment group for the Safety Population.

Table 10-3: Elevated Liver Function Criteria

Liver Function Parameter	Criteria
	\geq 3 × ULN
ALT	\geq 5 × ULN
ALI	$\geq 10 \times ULN$
	\geq 20 × ULN
	\geq 3 × ULN
AST	\geq 5 × ULN
ASI	$\geq 10 \times ULN$
	\geq 20 × ULN
ALT or AST	\geq 3 × ULN
	\geq 5 × ULN
	$\geq 10 \times ULN$
	\geq 20 × ULN
Total Bilirubin	$\geq 1.5 \times ULN$
	\geq 2 × ULN
Alkaline phosphatase	$\geq 1.5 \times ULN$
	\geq 2 × ULN
Combined Elevation in ALT or AST, and Total	ALT or AST \geq 3 × ULN, Total
Bilirubin	Bilirubin $\geq 1.5 \times ULN$
	ALT or AST $\geq 3 \times ULN$, Total
	Bilirubin ≥ 2 × ULN
Hy's Law	Concurrent evaluation ^a :
	ALT or AST $\geq 3 \times \text{ULN}$, Total
	Bilirubin $\geq 2 \times ULN$, and Alkaline phosphatase $\leq 2 \times ULN$
	phosphatase > 2 ^ OLN

^a Concurrent assessments: analytes may come from multiple samples taken within a 24-hour period.

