10.3 Vital Signs

Descriptive statistics for vital signs (eg, supine pulse rate, supine systolic and diastolic BP, body weight) values at baseline and changes from baseline values at each assessment visit, and at the end of the Open-label Treatment Period will be presented.

Vital sign values will be considered PCS if they meet the criteria for both the observed value and the change from baseline value listed in Table 10-4. The number and percentage of patients with PCS postbaseline vital sign values during Open-label Treatment Period will be tabulated for the Safety Population. The percentages will be calculated relative to the number of patients with an available baseline value and at least 1 postbaseline assessment. The numerator will be the total

Confidential Page 22 of 40

number of patients with an available baseline value and at least 1 PCS postbaseline vital sign value. A supportive listing of patients with PCS postbaseline values will be provided and will include the PID number and baseline and postbaseline values for each patient. A listing of all AEs for patients with PCS vital sign values will also be provided.

Table 10-4: Criteria for Potentially Clinically Significant Vital Signs

Vital Sion Danameter mit	Elaa	Criteria ^a					
Vital Sign Parameter, unit	Flag	Observed Value	Change From Baseline				
Supine Systolic blood pressure, mmHg	High	≥ 180	Increase of ≥ 20				
Supine Systone blood pressure, mining	Low	≤ 90	Decrease of ≥ 20				
Suning Digetalia blood procesure, mmHg	High	≥ 105	Increase of ≥ 15				
Supine Diastolic blood pressure, mmHg	Low	≤ 50	Decrease of ≥ 15				
Supine Pulse rate, bpm	High	≥ 120	Increase of ≥ 15				
Supine Fuise rate, opin	Low	≤ 50	Decrease of ≥ 15				
Waighth	High	_	Increase of ≥ 7%				
Weight ^b	Low	_	Decrease of ≥ 7%				

bpm = beats per minute.

The number and percentage of patients with orthostatic hypotension during the Open-label Treatment Period will be provided for the Safety Population. Orthostatic hypotension is defined as a reduction of ≥ 20 mm Hg in SBP or a reduction of ≥ 10 mm Hg in DBP while changing from the supine to standing position. A supportive listing of patients with orthostatic hypotension during the Open-label Treatment Period and Safety Follow-up Period will be provided. A listing of all AEs occurring in patients who experienced orthostatic hypotension will also be provided.

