15.2 Repeated or Unscheduled Assessments of Safety Parameters

For visits with repeated or unscheduled assessments of laboratory parameters, the non-missing values of the scheduled assessment will be used for summary statistics. If the scheduled assessments are missing, the last value from repeated or unscheduled assessments within the analysis window will be used for the visit. If repeated or unscheduled AIMS, BARS, SAS, vital signs or ECGs occur, apply the time-window rule and select the last non-missing values for each visit or endpoint.

All assessments during the Open-label Treatment Period will be included in PCS value determination and will be presented in the data listings.

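### SAP 15.2 guarantees use of all assessments only for PCS values: as written it can drop orthostatic falls that are followed by a normal repeat, and it leaves open which records enter the Table 10-3 liver and Hy's Law counts

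*SAP*

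**What the plan says.** SAP section 15.2 sets two selection rules and one exception.

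- Laboratory values: where a visit has repeats, "the non-missing values of the scheduled assessment will be used for summary statistics". If the scheduled value is missing, "the last value from repeated or unscheduled assessments within the analysis window will be used for the visit".
- AIMS, BARS, SAS, vital signs and ECGs: "apply the time-window rule and select the last non-missing values for each visit or endpoint".
- Exception: "All assessments during the Open-label Treatment Period will be included in PCS value determination and will be presented in the data listings".

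PCS is a defined term. SAP sections 10.2, 10.3 and 10.4 tie it to Table 10-2 (laboratory), Table 10-4 (supine blood pressure, supine pulse, weight) and Table 10-5 (ECG).

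Two further safety outputs are described separately and are not called PCS. For the liver criteria of Table 10-3, SAP 10.2 says: "The frequency and percentage of subjects with treatment-emergent elevated liver function values during the Open-label Treatment Period will be summarized". The Hy's Law row carries a footnote that "analytes may come from multiple samples taken within a 24-hour period". For orthostatic hypotension, SAP 10.3 says: "The number and percentage of patients with orthostatic hypotension during the Open-label Treatment Period will be provided for the Safety Population". It is defined there as a supine-to-standing fall of at least 20 mm Hg systolic or 10 mm Hg diastolic. Protocol 9.4.5.2 likewise lists the Hy's Law count apart from the PCS count. Neither output states its own record selection.

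**The concern.** Both outputs count patients who had the finding at any time in the Open-label Treatment Period. An any-time count needs every assessment. A one-value-per-visit rule can only discard qualifying records, and keeping the last value discards them in a particular direction, because a repeat tends to be taken when a reading looks abnormal and the repeat then replaces it.

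The primary objective is safety and tolerability, and these are incidence tables that a reader will use to judge it. What is at stake is an understated orthostatic hypotension rate. Depending on how a programmer reads the laboratory rule, higher-grade or combined liver elevations seen only on unscheduled samples may also be left out. Two programmers following the same SAP could produce different liver tables.

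**Working it through.** The plan gives no figure to reproduce. The check is a side-by-side reading, a literal application of 15.2 to invented records, and a scale calculation on assumed rates.

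**1. What the exception covers**

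| Output | Called PCS? | Records stated |
|---|---|---|
| Table 10-2 laboratory, Table 10-4 vital signs, Table 10-5 ECG | Yes | All assessments (15.2) |
| Table 10-3 liver criteria, including Hy's Law | No | Not stated |
| Orthostatic hypotension (10.3) | No | Not stated; the vital-sign rule in 15.2 is the only one that applies |

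Four criteria sit in both Table 10-2 and Table 10-3: ALT and AST at least 3 x ULN, bilirubin at least 2 x ULN, ALP at least 2 x ULN. Table 10-3 alone has ALT/AST at least 5, 10 and 20 x ULN, bilirubin and ALP at least 1.5 x ULN, the combined elevations and Hy's Law.

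**2. Orthostatic hypotension under the last-value rule**

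These are invented patients. I assume that each patient's readings share one window; the window tables were not legible in the text I had. Falls are systolic/diastolic in mm Hg.

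| Patient | Readings in time order | All assessments | Last value |
|---|---|---|---|
| A | 24/6, then repeat 8/3 the same day | Yes | No |
| B | Day 54 unscheduled 22/11, then Day 57 scheduled 5/2 | Yes | No |
| C | Day 57 scheduled 5/2, then Day 60 unscheduled 21/4 | Yes | Yes |
| D | 3/2 | No | No |

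The count is 3 of 4 with all assessments and 1 of 4 with the last value. If supine and standing readings stay paired, the selected records are a subset of all records, so the selected count can never be higher. But 15.2 selects values and does not say that the pair must come from one session. A mixed pair could err in either direction.

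**3. Table 10-3 under two readings of the laboratory rule**

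These are also invented patients (ALT in x ULN):

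- A: scheduled 2.1, unscheduled 3.4 three days later.
- B: scheduled 3.2, repeat 1.5.
- C: scheduled 2.8 with bilirubin 1.8; next-day repeat 4.0 with bilirubin 2.3 and ALP 1.0.
- D: scheduled value missing; unscheduled 3.6, then 1.2.
- E: 1.0.

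*Reading one:* the rule covers only by-visit descriptive statistics, so Table 10-3 uses everything. ALT at least 3 x ULN: A, B, C, D = 4 of 5. Hy's Law: C = 1.

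*Reading two:* the rule covers every tabulated count except PCS. ALT at least 3 x ULN: B = 1 of 5. Hy's Law: 0.

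The words summary statistics allow either reading. That the exception names only PCS favours reading two. The 24-hour footnote fits better with reading one, since it allows analytes from several samples to be combined.

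**4. Scale**

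N = 760 is the planned enrolment (Protocol synopsis). Let p be the proportion who ever meet a criterion and f the fraction of those who meet it only on unselected records. Neither is in the documents; both are assumptions.

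Reported count = N x p x (1 - f), and missing count = N x p x f. The relative understatement is f, whatever p is.

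| Output | p | N x p | Reported, f = 10% | Reported, f = 50% |
|---|---|---|---|---|
| Orthostatic hypotension | 2% | 15.2 | 13.7 | 7.6 |
| Orthostatic hypotension | 10% | 76 | 68.4 | 38 |
| ALT at least 3 x ULN, reading two only | 0.5% | 3.8 | 3.4 | 1.9 |
| ALT at least 3 x ULN, reading two only | 2% | 15.2 | 13.7 | 7.6 |

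Missing patients range from 15.2 x 0.1 = 1.5 to 76 x 0.5 = 38 for orthostatic hypotension, and from 3.8 x 0.1 = 0.4 to 15.2 x 0.5 = 7.6 for ALT.

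**The case against.** The other side has a good deal to say, mostly on the liver part.

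- **The laboratory rule speaks of summary statistics for visits.** That matches the by-timepoint descriptives in SAP 10.2, whereas Table 10-3 has no visit dimension. This stands: nothing in the SAP says that Table 10-3 is counted from scheduled samples.
- **The footnote is the more specific text.** It suggests that Hy's Law was never meant to be limited to one value per visit. This largely stands. It permits several samples and does not require them, and it does not say that unscheduled values are eligible, so it does not settle the other rows.
- **Severe values are not lost altogether.** Any ALT or AST at 5 x ULN or more also meets the PCS limit of 3 x ULN, so a patient with a non-PCS baseline is still counted in the PCS table and listed with AEs. This stands. What is at risk is placement in the higher and combined rows.
- **Hy's Law cases are known anyway.** Protocol 8.2.2 requires a laboratory alert and sponsor notification within 24 hours, and Protocol 6.4.2 provides quarterly safety review. This stands: surveillance is not affected.
- **Close monitoring does not show that peaks are missed.** Protocol 8.2.2 says that "close monitoring should be initiated in conjunction with the Study Physician", but for patients who already meet the criteria. It shows that unscheduled samples are expected, not that uncounted peaks usually fall on them.
- **Orthostatic repeats are unplanned.** Protocol 8.2.5 schedules one supine and one standing reading per visit, and SAP 10.3 lists affected patients and their AEs. This limits how often the problem arises. It does not remove it, because Protocol 8.4 allows unscheduled repeat assessments and the vital-sign rule carries no limit to summary statistics.

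**Conclusion.** The point holds with different strength in its two parts. For orthostatic hypotension, a stated rule followed literally can undercount an any-time safety outcome. For Table 10-3, including Hy's Law, the plan does not specify which records enter, and one of the two available readings would undercount. The loss is from the incidence tables, since 15.2 keeps every assessment in the listings.

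The size cannot be derived from the documents. It equals the unknown fraction f of affected patients whose qualifying readings are all unselected; the patient numbers above rest on assumed rates and on repeats sharing a window.

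Three stronger inferences are tempting and unsupported. A reader might conclude that values will certainly be dropped from the liver table, but the text allows the opposite reading. A reader might take the gaps between scheduled post-baseline laboratory visits (Days 8, 57, 113 and 183, so 49, 56 and 70 days), or one patient in 760 (0.13%), as the size of the loss. The first describes sampling frequency and the second is one patient as a percentage; neither measures dropped values. Finally, a reader might expect a common record rule to make the shared rows of Tables 10-2 and 10-3 agree. They could still differ, because the PCS denominator excludes patients with a PCS baseline, while treatment-emergent is not defined for Table 10-3.

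**What to change.** Reword the last sentence of SAP 15.2 along these lines:

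*Every assessment in the Open-label Treatment Period (scheduled, repeated, unscheduled and early termination) enters the determination of PCS values, of all Table 10-3 liver criteria including Hy's Law, and of orthostatic hypotension, using supine and standing values from the same session. The one-value-per-visit rules apply only to by-visit descriptive statistics.*

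If the sponsor also wants the shared rows of Tables 10-2 and 10-3 to be comparable, SAP 10.2 should define treatment-emergent and the denominator for Table 10-3. That is a separate addition.

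The cost is one sentence and the matching programming. No new data are needed, because all assessments are already collected and listed. The downside is that reported orthostatic and liver rates may be slightly higher. If the sponsor already intended to use all values, the change only records that intention.

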15.3 Missing Date of Open-Label Study Treatment

When the date of the last dose of open-label study treatment taken during the Open-label Treatment Period is missing for a patient in the Safety Population, all efforts should be made to obtain the date from the Investigator. If it is still missing after all efforts, then the last known dose date will be set as the date of the last dose of open-label study treatment.

Confidential Page 33 of 40

15.4 Missing Severity Assessment for Adverse Events

If severity is missing for an AE that started before the date of the first dose of open-label study treatment, then a severity of *mild* will be assigned. If the severity is missing for an AE that started on or after the date of the first dose of open-label study treatment, then a severity of *severe* will be assigned. The imputed values for severity assessment will be used for the incidence summary; while the actual values will be presented in the data listings.

15.5 Missing Relationship to Investigational Product for Adverse Events

If the relationship to open-label study treatment is missing for an AE that started on or after the first dose date of open-label study treatment, a causality of *yes* will be assigned. The imputed values for relationship to open-label study treatment will be used for the incidence summary, while the actual values will be presented in the data listings.

15.6 Missing Date Information for Adverse Events

The following imputation rules apply only to cases in which the start date is incomplete (ie, partially missing) for AEs.

Missing month and day

- If the year of the incomplete start date is the same as the year of the date of the first dose of open-label study treatment, then the day and month of the date of the first dose of open-label study treatment will be assigned to the missing fields;
- If the year of the incomplete start date is before the year of the date of the first dose of openlabel treatment, then December 31 will be assigned to the missing fields;
- If the year of the incomplete start date is after the year of the date of the first dose of openlabel study treatment, then January 1 will be assigned to the missing fields.

Missing month only

• If only the month of the incomplete start date is missing, the day will also be treated as missing, and both the month and day will be replaced according to the procedure described above.

Missing day only

- If the month and year of the incomplete start date are the same as the month and year of the date of the first dose of open-label study treatment, then the day of the date of the first dose of open-label study treatment will be assigned to the missing field;
- If either the year of the incomplete start date is before the year of the date of the first dose of open-label study treatment or the years are the same but the month of the incomplete start date is before the month of the date of the first dose of open-label study treatment, then the last day of the month will be assigned to the missing field;

Confidential Page 34 of 40

• If either the year of the incomplete start date is after the year of the date of the first dose of open-label study treatment or the years are the same but the month of the incomplete start date is after the month of the date of the first dose of open-label study treatment, then the first day of the month will be assigned to the missing field.

If the stop date is complete and the imputed start date, when imputed as instructed above, is after the stop date, then the start date will be imputed to equal the stop date.

If the start date is completely missing and the stop date is complete, then use the following algorithm to impute the start date:

- If the stop date is on or after the date of the first dose of open-label study treatment, the date of the first dose of open-label study treatment will be assigned to the missing start date;
- If the stop date is before the date of the first dose of open-label study treatment, the stop date will be assigned to the missing start date.

15.7 Missing Date Information for Prior or Concomitant Medications

For prior or concomitant medications, including psychotropic medications, incomplete (ie, partially missing) start dates and/or stop dates will be imputed. If the start date and the stop date for a patient are both incomplete, the start date will be imputed first.

15.7.1 Incomplete Start Date

The following rules will be applied to impute the missing numeric fields. If the stop date is complete and the imputed start date is after the stop date, then the start date will be imputed using the stop date.

Missing month and day

- If the year of the incomplete start date is the same as the year of the date of the first dose of open-label study treatment, then the month and day of the date of the first dose of open-label study treatment will be assigned to the missing fields;
- If the year of the incomplete start date is before the year of the date of the first dose of openlabel study treatment, then December 31 will be assigned to the missing fields;
- If the year of the incomplete start date is after the year of the date of the first dose of openlabel study treatment, then January 1 will be assigned to the missing fields;

Missing month only

• If only the month of the incomplete start date is missing, the day will also be treated as missing, and both month and day will be replaced according to the procedure described above.

Confidential Page 35 of 40

Missing day only

- If the month and year of the incomplete start date are the same as the month and year of the date of the first dose of open-label study treatment, then the day of the date of the first dose of open-label study treatment will be assigned to the missing field;
- If either the year of the incomplete start date is before the year of the date of the first dose of open-label study treatment or the years are the same but the month of the incomplete start date is before the month of the date of the first dose of open-label study treatment, then the last day of the month will be assigned to the missing field;
- If either the year of the incomplete start date is after the year of the date of the first dose of open-label study treatment or the years are the same but the month of the incomplete start date is after the month of the date of the first dose of open-label study treatment, then the first day of the month will be assigned to the missing field.

15.7.2 Incomplete Stop Date

The following rules will be applied to impute the missing numeric fields. If the imputed stop date is before the start date (imputed or non-imputed), then the imputed stop date will be equal to the start date.

Missing month and day

- If the year of the incomplete stop date is the same as the year of the date of the last dose of open-label study treatment, then the month and day of the date of the last dose of open-label study treatment will be assigned to the missing fields;
- If the year of the incomplete stop date is before the year of the date of the last dose openlabel study treatment, then December 31 will be assigned to the missing fields;
- If the year of the incomplete stop date is after the year of the date of the last dose of openlabel study treatment, then January 1 will be assigned to the missing fields.

Missing month only

• If only the month of the incomplete stop date is missing, the day will also be treated as missing, and both month and day will be replaced according to the procedure described above.

Missing day only

- If the month and year of the incomplete stop date are the same as the month and year of the date of the last dose of open-label study treatment, then the day of the date of the last dose will be assigned to the missing field;
- If either the year of the incomplete stop date is before the year of the date of the last dose of open-label study treatment or if the years are the same but the month of the incomplete stop date is before the month of the date of the last dose of open-label study treatment, then the last day of the month will be assigned to the missing field;

Confidential Page 36 of 40

• If either the year of the incomplete stop date is after the year of the date of the last dose of open-label study treatment or the years are the same but the month of the incomplete stop date is after the month of the date of the last dose of open-label study treatment, then the first day of the month will be assigned to the missing field.

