6.3 Study Population

6.3.1 Inclusion Criteria

In addition to the Inclusion Criteria below, patients will be checked for previous participation in an ITI-007 clinical study and for duplicate enrollment by study site staff through Verified Clinical Trials (VCT).

Each patient entering the Open-label Safety Study must meet all of the following criteria:

- 1. In the opinion of the Investigator, the patient must have safely completed the lead-in study.
- 2. The patient must understand the written informed consent for the Open-label Safety Study, provide signed and witnessed written informed consent.
- 3. The patient is taking his/her ADT as prescribed from the lead-in study.
- 4. The patient must agree to continue using highly effective methods of birth control as specified in the lead-in study through the Safety-Follow-up Period of the Open-label Safety Study, or female patients or female partners of male patients must be of non-childbearing potential.

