8.3 Prior and Concomitant Medication

Prior medication is defined as any medication taken before the date of the first dose of open-label lumateperone. *Prior concomitant medication* is any medication that started before the date of the first dose of open-label lumateperone and stopped or is ongoing after the date of the first dose of open-label lumateperone. *Concomitant* medication is defined as any medication taken on or after the date of the first dose of open-label study drug.

Prior, prior concomitant, and concomitant medication use will be summarized as the number and proportion of patients who received each prior, prior concomitant, and/or concomitant medication within each therapeutic class and preferred term. Multiple medications used by a patient will only be counted once.

Any medication that started after the date of the last dose of open-label lumateperone will not be included in the summary but will be included in the patient data listings.

Confidential Page 16 of 40

9. EFFICACY ANALYSES

The efficacy analyses will be based on patients in the Safety Population with an available baseline efficacy value and at least one postbaseline efficacy assessment during the Open-label Treatment Period. Baseline is defined as the last measurement prior to the first dose of double-blind treatment during the lead-in studies (Studies ITI-007-501 and ITI-007-502).

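### SAP 15.7 lets an imputed medication start override a recorded stop month, so some drugs that ended before open-label lumateperone are counted as concomitant and not as prior (minor)

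*SAP*

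**What the plan says.** SAP 15.7 sets the order of work: "If the start date and the stop date for a patient are both incomplete, the start date will be imputed first".

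SAP 15.7.1 deals with the start. If only the year is known and it equals the year of the first open-label dose, "then the month and day of the date of the first dose of open-label study treatment will be assigned to the missing fields". A year-only start in an earlier year goes to 31 December of that year. The one safeguard begins "If the stop date is complete and the imputed start date is after the stop date", in which case the start is taken from the stop. It does not mention a partial stop.

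SAP 15.7.2 deals with the stop. A stop without a day, in a month before the month of the last open-label dose, becomes the last day of the recorded month. Any conflict is then settled in favour of the start: "If the imputed stop date is before the start date (imputed or non-imputed), then the imputed stop date will be equal" to the start date.

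SAP 8.3 uses these dates. "Prior medication is defined as any medication taken before the date of the first dose of open-label" lumateperone. A prior concomitant drug started before the first open-label dose and stopped, or is ongoing, after it. A concomitant drug was taken on or after that date.

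For background ADT, Protocol 6.3.1, inclusion criterion 3, reads "The patient is taking his/her ADT as prescribed from the lead-in study".

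**The concern.** A recorded month is data, while a start date filled in from a bare year is a guess. The complete-stop check in 15.7.1 shows that recorded stops are meant to limit imputed starts. When the stop lacks only its day, the order is reversed and the guess displaces the record. A drug known to have ended before open-label lumateperone then enters the concomitant table and leaves the prior table.

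The ADT case comes from the same start rule and needs no stop date. Criterion 3 establishes that the background ADT was already being taken in the lead-in, yet a year-only start in the first-dose year is dated to the first open-label dose. At stake is the accuracy of the prior, prior-concomitant and concomitant counts in a study of an adjunctive treatment.

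**Working it through.** The plan states no figure on this point, so the check applies its rules in order. The dates are illustrative: first open-label dose 15 Jun 2022, last dose 13 Dec 2022 (182 days inclusive).

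**Main case: start recorded as 2022, stop recorded as March 2022**
1. Start first (15.7): the year equals the first-dose year, so the start is 15 Jun 2022 (15.7.1).
2. The 15.7.1 safeguard is skipped because the stop is not complete.
3. Stop (15.7.2): March precedes December, the last-dose month, so the stop is 31 Mar 2022.
4. 31 Mar is before 15 Jun, so the stop is reset to 15 Jun 2022.
5. SAP 8.3: the start is not before the first dose, so the drug is neither prior nor prior concomitant. It is dated to the first-dose day, so it is concomitant.

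The latest stop that the record allows is 31 Mar, which is 30 (April) + 31 (May) + 15 (June) = 76 days before the first open-label dose.

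**Variants with the same dosing dates**

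| Recorded start | Recorded stop | Start used | Stop used | Class |
|---|---|---|---|---|
| 2022 | Mar 2022 | 15 Jun 2022 | 31 Mar, reset to 15 Jun 2022 | concomitant only; contradicts the record |
| 2022 | 20 Mar 2022 | 20 Mar 2022 | 20 Mar 2022 | prior |
| 2021 | Mar 2022 | 31 Dec 2021 | 31 Mar 2022 | prior |
| Feb 2022 | Mar 2022 | 28 Feb 2022 | 31 Mar 2022 | prior |
| 2022 | Jun 2022 | 15 Jun 2022 | 30 Jun 2022 | concomitant only; record does not contradict |
| 2022 | 2022 | 15 Jun 2022 | 13 Dec 2022 | concomitant only; record does not contradict |
| 2022 (background ADT) | ongoing | 15 Jun 2022 | none | concomitant only; contradicts criterion 3 |

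Treatment that spans two calendar years gives the same result. With first dose 10 Nov 2022 and last dose 10 May 2023, the main case ends with start and stop both on 10 Nov 2022.

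The stop-date failure therefore needs three conditions together: a year-only start in the first-dose year, a stop with month and year but no day, and a stop month before the first-dose month. When all three hold, the result follows from the rules for any first-dose date. When any one fails, the class does not contradict the record. The ADT failure needs only a year-only start in the first-dose year. An ADT start in an earlier year goes to 31 December and stays both prior and prior concomitant.

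**With the start capped at the end of the recorded stop month**, the main case becomes start = stop = 31 Mar 2022, classed as prior. Capping the ADT start at 14 Jun 2022 restores it to the prior and prior-concomitant counts and keeps it concomitant.

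**The case against.** The strongest reply is that the failure is narrow and nothing depends on it. It needs an unusual combination of partial dates. Protocol 10.3.2 provides edit checks for completeness and logic, with site queries, so some partial dates should be resolved before lock. The Safety Population, the efficacy set and treatment-emergent status do not use the medication class, and no test is planned. Placing an uncertain date on treatment also matches the cautious defaults in SAP 15.4 and 15.5. All of this stands on size. It does not rescue the rule, because a cautious default is reasonable only when no recorded fact contradicts it. Here a recorded month does, and the drug is also lost from the prior table.

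Several stronger readings are tempting, but the documents do not support them:
- **Adverse events.** SAP 15.6 has a similar safeguard, "If the stop date is complete and the imputed start date, when imputed as instructed above, is after the stop date", so a reader might infer that pre-treatment events become treatment-emergent. AEs are collected from open-label consent (Protocol 8.2.1.4), which is obtained on Day 1, when drug is dispensed (8.4.1). Such an event could hardly stop in a month before the first dose. Neither document says that events which ended in the lead-in are analysed here.
- **Prohibited medication.** A reader might infer that misdated psychotropics would count as deviations under Protocol 7.8.2. SAP section 6 takes major deviations from a separate management plan, and nothing says imputed dates feed it.
- **ADT shown as newly started.** SAP 8.3 tabulates counts by class and preferred term, not start dates, so no planned table would show this.
- **Stopped before any lumateperone.** Protocol 6.2.1 says patients start or continue lumateperone, so the statement holds only for open-label lumateperone.
- **Frequency.** That the rule fails every time its conditions are met is a property of the rule. It says nothing about how often they are met.

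**Conclusion.** The rule is wrong as written, and the point is minor. Read literally, SAP 15.7.1 and 15.7.2 let an imputed start override a recorded stop month under the three conditions above. They also leave some background ADT out of the prior and prior-concomitant counts. Both errors lower those counts, and the stop-date error also raises the concomitant count. Only the descriptive medication summaries change.

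The number of affected records cannot be derived: neither document gives a rate of partial dates or the distribution of ADT start dates. The conclusion assumes that the rules will be programmed as worded. SAP 15.4, 15.5 and 15.8 say that actual values will appear in the listings, whereas 15.7 is silent, so a reader may not be able to see that a stop month was moved.

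**What to change.** Make three changes to SAP 15.7:
1. In 15.7.1, replace the complete-stop condition with: *An imputed start may not be later than the stop date or, if the stop is partial, than the latest date its recorded month or year allows; if it is, use that date as the start.*
2. In 15.7.2, add: *A recorded stop month or year is not changed to agree with an imputed start.*
3. For background ADT carried over from the lead-in, add: *The imputed start is no later than the day before the first open-label dose.*

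Keep the third rule to background ADT. Visit 8 of the lead-in and Visit 1 of this study are the same visit, so a cap on every drug recorded in the lead-in could force a drug begun that day into the prior class.

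The cost is three sentences and a small programming change. No new data are needed.
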